Our preliminary data has shown: (1) elevated blood cytokine concentrations during the acute phase of trauma are correlated with the development of fatal post-traumatic complications [8], (2) that early administration of a non-steroidal anti-inflammatory drug (NSAID) resulted in decreased blood serum levels of IL-6, Prostaglandin E2 (PGE2), improved pulmonary edema, and enhanced arterioles ability to vasoconstrict in response to hemorrhage in animal models [9], and (3) that the addition of the internal physiologic parameters (inflammatory cytokines) to New Injury Severity Score (NISS – a marker of the external anatomical insult) significantly improves the ability to predict hospital length of stay of trauma patients when compared to NISS alone [10]. Our group is the first to use an integrative approach that combines the external anatomic injury data with the internal physiologic response for accurate prediction of patient's clinical outcome. Therefore, if we apply this same mindset to treatment, we can improve the trauma patients' care by addressing both parameters as opposed to solely focusing on the external injury as done in the past. Our ability to modify post-traumatic physiologic response via short-term administration of a NSAID may lead to improved patient outcome.

Over the last decade, clinicians remain puzzled over the safety of NSAID administration after fracture in terms of bone union [11-15]. In addition, given the current landscape for opioid epidemic in the United States [16, 17], alternative non-opioid pain management during acute trauma has the potential to reduce opioid consumption and represents a pivotal component of multimodal analgesia strategy.

Objectives

List your research objectives. Please include a summary of intended research objectives in the box below.

Aim 1: Determine if a brief and low dose scheduled administration of an NSAID (Ketorolac) will reduce the inflammatory cascade and improve the clinical outcomes of orthopaedic trauma patients. Ketorolac will be used as the NSAID of choice because it is of low cost to patients, readily available intravenously, has few side effects, and also decrease opioid consumption in acute trauma [18-21].

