Aim 1: The study population will consist of 200 patients (100 control, 100 treated with Ketorolac) that are admitted to the inpatient surgical service at our level I trauma centers for management of orthopedic trauma care. All trauma patients that are between the ages of 18-75 and with NISS > 9 (moderate injury) [33, 34] will be enrolled and treated according to the standard Advance Trauma Life Support (ATLS) protocol. 100 patients in the control group will receive placebo intravenous saline every 6 hours for their initial 5 days of hospitalization and no NSAID administration. 100 patients randomized to the treatment group will receive 15 mg of Ketorolac every 6 hours for their initial 5 days of hospitalization. A daily blood sample (10 cc) will be collected on Days 1–5 by blinded health care personnel. These blood samples will be analyzed via sandwich ELISA method for concentrations of IL-1, IL-6, IL-10, and PGE2. Serum concentrations will be compared between the treatment and control groups using two-tailed independent t-tests. In addition to the standard trauma labs, patient demographics, injury data (gender, age, BMI, mechanism of injury, NISS, and types of surgical/procedural interventions), injury outcomes (incidence of bacterial pneumonia, ARDS, SIRS, MODS), complications defined in the National Trauma Dataset, and inflammatory data will be compiled, tracked, and maintained in our clinical database (REDCap). Outcome variables (hospital and ICU length of stay and occurrence of pneumonia and/or ARDS and/or SIRS or death), and the predictor variables of interest (inflammatory markers and NISS) will be compared using Poisson regression. The odds of developing post traumatic complications in the different predictor groups will be determined using multiple logistic regressions. The covariates will be adjusted for in the regression models: age, sex, injury severity, severity of head and/or extremity injury, injury mechanism, and injury outcome.

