Patients with pre-existing medical co-morbidities and contraindications to ketorolac will be excluded from the study (see 5 for detailed exclusion criteria)

Patients in the treatment group will receive 15 mg IV ketorolac every 6 hours for 5 days after admission.

e. **Post-operative inpatient care:** Enrolled patients will have daily blood samples (10 cc) will be collected post-admission and at 24 hours intervals for 5 days by blinded health care personnel. The initial blood sample will be collected within 12 hours of initial injury and before the first scheduled administration of ketorolac to establish baseline cytokine profile. Subsequent blood sample collection will be 24 hours apart. Medication compliance and monitoring will be performed daily by the same research coordinators.

Sandwich ELISA will be used to determine the concentrations of IL-1, IL-6, IL-10, and PGE2 in obtained blood samples. Blinded quality control samples will be included in every batch for each ELISA assay. This will allow for the calculation of coefficient of variation (CV) within and across patient cohorts. In the present study, the CV will be calculated for IL-1, IL-6, IL-10, and PGE2. If wide variations are observed among the analytes during the analysis, we will restrict our analysis to analytes in which the CV is less than 20%.

In addition to the standard trauma labs (Sodium, Potassium, Creatinine, Lactic acid, Glucose, Platelet, blood urea nitrogen (BUN), hematocrit, and white blood cell count), patient demographics (sex, age, and BMI), injury data (mechanism of injury, NISS, and types of surgical/procedural interventions), posttraumatic complications (occurrence of bacterial pneumonia, ARDS, SIRS, MODS), complications defined in the National Trauma Dataset, and inflammatory data will be collected. This data will be maintained in our clinical database (REDCap) by a full-time Clinical Study Coordinator.

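### The Aim 1 regressions adjust NISS for an undefined injury severity term and complications for injury outcome, and may put about 12 terms on few events

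*Combined protocol and SAP*

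**What the plan says.** The models are set out in the IRB application, Research Description, Research Procedures, Aim 1.

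- Outcomes: "hospital and ICU length of stay and occurrence of pneumonia and/or ARDS and/or SIRS or death". For these, "the predictor variables of interest (inflammatory markers and NISS) will be compared using Poisson regression".
- Complications: "The odds of developing post traumatic complications in the different predictor groups will be determined using multiple logistic regressions".
- Covariates in the regression models: "age, sex, injury severity, severity of head and/or extremity injury", followed by injury mechanism and injury outcome.
- Markers: "concentrations of IL-1, IL-6, IL-10, and PGE2", sampled daily on Days 1-5. The day or summary that enters the models is not stated.

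The Background calls NISS the "New Injury Severity Score (NISS – a marker of the external anatomical insult". Protocol section 10, item e, lists for collection "injury data (mechanism of injury, NISS, and types of surgical/procedural interventions". The Aim 1 list likewise names NISS and no other severity score. Earlier in the Aim 1 paragraph, injury outcomes is the label for the incidence of bacterial pneumonia, ARDS, SIRS and MODS.

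Protocol section 3 makes complications a secondary outcome. Protocol section 7 has no logistic or Poisson model: log length of stay (LOS) is compared by analysis of variance, and cytokines, pain scores and opioid use by linear mixed models. Covariates there are limited to demographics. Its Fisher exact tests for categorical variables could at most compare crude complication rates between arms.

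The sample size is 200 in Aim 1 and 112 in protocol sections 6 and 10. The continuation review records 108 enrolled, and the screening comments of August 2023 describe the study as closed to enrolment.

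**The concern.** There are three separate difficulties in one covariate list.

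1. NISS is a predictor of interest and is itself the trial's injury severity score, yet the same models adjust for injury severity. An analyst cannot fit this without inventing a definition.
2. Adjusting a model of pneumonia, ARDS, SIRS or death for injury outcome, in the sense the paragraph gives that term, puts near copies of the outcome among the predictors. The marker and NISS coefficients then no longer describe the risk of complications.
3. The list is long for a trial sized on LOS. With few events per term, maximum-likelihood logistic regression pushes true non-zero log odds ratios away from zero on average.

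At stake is the only regression specified for complications, and so any statement that a marker or NISS predicts them.

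**Working it through.** **The plan's own figure.** No event rate, event count or term count is given for these regressions. The only calculated sample size is for LOS (protocol section 6), and it reproduces: n per group = 2 × (1.96 + 0.8416)² × 1.5² / 0.928² = 41.01, rounded up to 42. Then 84 / (1 − 0.25) = 112.

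**NISS and a second severity score.** With two correlated predictors, the standard error is multiplied by √[1/(1 − r²)]. The correlations are assumed.

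| r | 1/(1 − r²) | SE multiplied by |
|---|---|---|
| 0.80 | 2.78 | 1.7 |
| 0.90 | 5.26 | 2.3 |
| 0.95 | 10.26 | 3.2 |

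If injury severity simply means NISS, the second column is redundant. Dropping it leaves one NISS term and does not change the fitted values or marker odds ratios.

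**Terms.** 4 markers + NISS + age + sex + injury severity + head + extremity + mechanism + injury outcome = 12 at one degree of freedom each. The count is 11 if head and extremity form one term, and 13 or more if mechanism or outcome has several levels. It assumes that all markers enter together, which the text does not say.

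**Events per term.** Events = N × assumed rate, divided by 12.

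| N | Events at 20% | Events at 30% | Per term |
|---|---|---|---|
| 84 (evaluable, section 6) | 16.8 | 25.2 | 1.4-2.1 |
| 108 (enrolled) | 21.6 | 32.4 | 1.8-2.7 |
| 112 (section 6 target) | 22.4 | 33.6 | 1.9-2.8 |
| 200 (Aim 1) | 40 | 60 | 3.3-5.0 |

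Over a wider assumed range of 10-40%, the figures are 0.7-2.8 (N=84), 0.9-3.7 (N=112) and 1.7-6.7 (N=200). Ten events per term would need 120 events, which is more than 112 patients and 60% of 200.

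**Size of the bias, by simulation.**

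- 12 terms, true odds ratio 1.8 per SD for one marker, event rate 20-30%: ordinary logistic regression overstates the mean log odds ratio by about 17-39% at N=84-112 and 8-9% at N=200. Firth's fit stays within about 5%.
- The mean is pulled up by skew. In one such run the median odds ratios were 2.07 (N=84, 20%), 2.01 (N=108, 20%) and 1.96 (N=108, 30%). On the log scale, against ln 1.8 = 0.588, these are about 24%, 19% and 14% too high.
- Correlated terms and a true odds ratio of 1.5, at 20% and 30%: +33% and +27% at N=84, +19% and +16% at N=112, +10% and +11% at N=200. At the 20% rate, 7.1% of fits failed at N=84 and 2.3% at N=112.
- In that second set, markers with no effect were rejected in 4.9-7.0% of runs.
- Raising the severity correlation from 0.80 to 0.95 (N=112, 30%) moved the marker inflation only from 16% to 18%. The marker bias comes from sparse events, not from the severity overlap.

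**After the change.** One marker, NISS, age, sex and arm make 5 terms: 16.8/5 to 33.6/5 = 3.4-6.7 events per term at N=84-112, and 40/5 to 60/5 = 8-12 at N=200. With 5 terms, ordinary logistic regression still overstates by 10-15% at N=84-108. Firth's fit gives median odds ratios of 1.77-1.81 against a true 1.8.

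**The case against.** The strongest reply is that the Aim 1 paragraph may not govern. The application refers to the protocol for the full design, and protocol section 7 contains no such models. That stands as a reason to reconcile the two texts. It does not dispose of the point: the paragraph remains in the application, and section 7 supplies no complication model to replace it.

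The 12-term model is also a reading, not a statement. The plan speaks of several regressions and of predictor groups, and fitting one marker at a time is compatible with its words. Ordinary maximum likelihood is likewise inferred from silence. Both stand, so the sparse-event figures are conditional.

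The choice of N matters as well. At Aim 1's own 200 patients the bias is near 10%, well below the figures for 84-112. That stands too, although the recorded enrolment of 108 points to the lower range.

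Head-injury severity may be a distinct confounder, since the consent sections expect more than 30% of patients to have traumatic brain injury. This is a fair reason not to insist on removing it.

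A reader might infer that the NISS effect is uninterpretable or the model impossible to fit. The documents do not support that. A duplicate NISS column is simply redundant, and a distinct second score leaves a conditional effect that is imprecise and hard to read but still defined.

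**Conclusion.** The point holds in limited form. Two defects rest on the text itself: injury severity is undefined beside NISS, and injury outcome, as the paragraph uses the term, repeats the complications being modelled. The third, too many terms for the events, depends on all markers entering together and on an assumed 20-30% event rate. Under those assumptions a marker with a true odds ratio of 1.8 has its mean log odds ratio overstated by about 17-39% at N=84-112 and 8-9% at N=200.

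A reader might conclude that every marker odds ratio is overstated. That does not follow: the bias concerns markers with a real effect, and null markers are not biased on average. Nor does the events-per-term argument reach the Poisson models of hospital and ICU LOS, which use all patients. A reader might also think that the primary result or Aim 1 as a whole is compromised. The randomised LOS comparison in protocol section 7 does not use these models, and Aim 1 asks about the effect of ketorolac. The finding that cytokines add to NISS is cited as preliminary data on predicting LOS. This is a minor but easily corrected weakness in a secondary analysis.

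**What to change.** In the Aim 1 paragraph:

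- Delete injury severity from every model that contains NISS.
- Delete injury outcome from the complication models.
- Fit the complication models one marker at a time with NISS, age, sex and treatment arm, using Firth's penalised logistic regression. Head-injury severity may be kept as one further term. Rewrite the covariate sentence to match, so that extremity severity and mechanism do not remain listed for a model that omits them.
- State which day's marker value, or which summary, is used.

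Carry this complication model into protocol section 7 and state whether N is 200 or 112.

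The cost is wording and one procedure option, with no new data. The downside is that no single model holds all four markers together, so their separate contributions are not mutually adjusted.

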If your study is monitored by a DSMB or under a DSMP, attach all documentation (i.e. summary report; meeting minutes) representing Data and Safety Monitoring activities that have not been previously reported to the IRB.

Attachments

7. Since the most recent IRB Initial/Continuation Review Approval:

Have there been any **participant complaints** regarding the research?

Yes No

If yes, in the field below, provide a summary describing the complaints.

Have any **subjects withdrawn** from the research voluntarily or by you as the PI for reasons related to safety, welfare, or problems related to the conduct of the research? If a participant does not meet the screening criteria for a study even if they signed a screening consent it is NOT considered a withdrawal.

Yes No

If yes, in the field below, provide a detailed explanation to the withdrawal(s) including if participants were lost to contact.

Has any **new and relevant literature** been published since the last IRB review, especially literature relating to risks associated with the research?

Yes No

If yes, attach a copy of the literature as well as a brief summary of the literature including, if pertinent, the impact of the findings on the protection of human subjects.

Attachments

Have there been any **interim findings**?

Yes No

If yes, attach a copy of **Interim Findings**.

Attachments

Attach Type	File Name
Interim Findings	OTA IM Abstract VAS and MME 2.10.23.docx

Have **subjects experienced any benefits**?

Yes No

If yes, in the field below, provide a description of benefits subjects have experienced.

Results:

In total, 70 participants were enrolled, with 35 randomized to the ketorolac group and 35 to the placebo group. Study groups were balanced with respect to age, BMI, and NISS. Over the 5-day treatment period, average opioid intake ($p = 0.0039$) and VAS pain scores ($p = 0.0481$) were significantly reduced in the ketorolac group compared to the placebo group. The ketorolac group experienced a 43.2% reduction in mean MME compared to the placebo group.

Conclusion:

Scheduled, short-term use of low-dose ketorolac was associated with significantly reduced opioid use and pain in orthopedic polytrauma patients with no apparent short-term adverse effects. The results support the use of low-dose short-term schedule ketorolac for pain control among orthopaedic polytrauma patients.

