Aim 2: The enrolled patients will be followed daily by our trained clinical research coordinator. Patient's subjective pain scores will be assessed and documented by the trained nursing staff using Visual Analogue Scale (VAS) daily. Morphine milligram equivalent (MME) along with other pain medication intake will be recorded per day for the duration of Ketorolac or placebo therapy. Patient's clinical course will be monitored closely and daily to ensure no NSAIDs will be administered to the control cohort to ensure consistency and protocol adherence of the study. Once patients are discharged from the hospital, outpatient pain scores will be assessed during routine clinic follow up visits using Patient-Reported Outcomes Measurement Information System (PROMIS) surveys. Opioid and pain modulating medication prescription refills will be monitored using the State All Scheduled Prescription Electronic Reporting system. Patient narcotic requirement will be assessed during all of the routine follow up visits by the same research coordinator in order to maintain consistency. Patients' inpatient and outpatient subjective pain score and MME intake will be compared between the control and treatment groups using two-tailed independent t-tests.

Aim 3:

Finally, analysis will be performed to evaluate the treatment effects between two groups using fracture unions as a dependent variable. The rate of fracture unions will be calculated at 3 month, 6 month and 12 month. Fractures will be considered united if they met the criteria for clinical or radiological union. The baseline clinical factors that are independently associated with fracture unions will be assessed from candidate variables and are entered using a forward ($p<0.05$) and backwards ($p<0.10$) stepwise selection procedure. Finally, the multivariate model will be performed to assess the association of clinical factors with fracture unions starting at 3 month between two groups.

Attachments

Data Collection & Research Materials

In this section, please provide the following:

- Describe all sources or methods for obtaining research materials about or from living individuals (such as specimens, records, surveys, interviews, participant observation, etc.), and explain why this information is needed to conduct the study.
- For each source or method described, please list or attach all data to be collected (such as genetic information, interview scripts, survey tools, data collection forms for existing data, etc.).

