Group-level summary statistics will be calculated for demographic and clinical variables, and differences between the 2 groups will be evaluated using two-sample t-tests for quantitative measures and Fisher exact tests for categorical measures, as appropriate. LOS and MME values will be summarized using medians and interquartile ranges for each group. Group-level VAS pain scores will be summarized using means and standard deviations. An analysis of variance model will be fit to compare log-transformed LOS between the 2 groups. Linear mixed models will be used to estimate differences in VAS pain scores and log-transformed MME values over time between the 2 groups. Time and group comparisons for each cytokine will be made using linear mixed models, with and without adjusting for selected covariates. Patient demographic variables will be considered for inclusion as covariates in each model but will only be retained if they significantly improve the model. Linear mixed models may be log-transformed, double-log-transformed, or square-root-transformed to correct for right skewness, as appropriate. Likelihood ratio testing and Akaike information criterion will be used to select appropriate covariance structures in each case. A Kenward–Roger adjustment will be used to correct for negative bias in the standard errors and degrees of freedom calculations. Throughout the study, a P value of less than 0.05 will be considered significant. All analyses will be completed in SAS 9.4 (SAS Institute Inc.; Cary, NC).

8. Study-Wide Recruitment Methods

Potential patients will be prospectively identified either at the time of the initial consultation, at the morning fracture conference, based on the orthopaedic injury diagnosis (inclusion criteria noted above). Patients will be screened by their inclusion and exclusion criteria and will be considered for enrollment in the study should they meet study criteria.

9. Study Timeline

After arrival, patient screening and enrollment is expected within 12 hours of arrival to ensure initial blood draw. Further participation of subjects will include blood draws and ketorolac administration through day 5. Patient participation will continue through to their follow-up visits and conclude with their 6 weeks post discharge clinic visit. Detailed project timeline and schedule of activities is listed in Table 1.

Tentative time table of the proposed project												
Procedures	Enrollment	Inpatient						Outpatient				

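### Aim 3 has no rule for several fractures in one patient and picks covariates by p-value; if fractures are analysed as independent, the between-arm standard error may be too small

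*Combined protocol and SAP*

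**What the plan says.** The analysis is described in the IRB application, Research Description, Research Procedures, Aim 3. Treatment is evaluated "using fracture unions as a dependent variable". The definition is worded per fracture: "Fractures will be considered united if they met the criteria for clinical or radiological union". The summary is also in terms of fractures: "The rate of fracture unions will be calculated at 3 month, 6 month and 12 month".

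Covariates come from the data: "The baseline clinical factors that are independently associated with fracture unions will be assessed from candidate variables", and these "are entered using a forward ($p<0.05$) and backwards ($p<0.10$) stepwise selection procedure". Last, "the multivariate model will be performed to assess the association of clinical factors with fracture unions starting at 3 month between two groups".

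Aim 3 does not state the denominator of the rate, a rule for a patient with more than one fracture, the type of model, how the three visits enter it, or any allowance for correlation within a patient. The protocol does not fill these gaps. Section 7 (Statistical Analysis Plan) covers length of stay, pain, opioid use and cytokines, and does not mention union.

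**The concern.** Patients are randomised. If one patient contributes several fractures, they share age, comorbidity, injury energy and treatment, so their healing is likely to be correlated. A model that treats each fracture as an independent observation overstates the information on the treatment effect.

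Several fractures per patient are plausible here. The consent text describes high-energy mechanisms, and the interim abstract in the continuation review reports results in "significantly reduced opioid use and pain in orthopedic polytrauma patients" (with the word polytrauma in its own description of the cohort).

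The stepwise step is a separate weakness. A randomised comparison does not need it, and it leaves the adjusted model unknown until the data are seen.

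Bone healing is the NSAID risk discussed both in the application (Potential Risks & Benefits) and in protocol section 15. Both say the trial will evaluate union rates. An interval that is too narrow could show a false harm signal or give reassurance that the data do not support.

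**Working it through.** **The plan's own figure.** No sample size or power is given for union. The only calculation is for length of stay (protocol section 6): difference 0.928 days, SD 1.5 days, alpha 0.05 (two-sided assumed), power 80%. A two-sample t-test needs 41.995, so 42 per group, and 84/(1 − 0.25) = 112. Both figures reproduce, but they say nothing about union.

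**Clustering.** Nominal alpha comes from protocol section 7: "Throughout the study, a P value of less than 0.05 will be considered significant". The mean number of fractures per patient (m) and the ICC are not in the documents, so both are assumed.

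- Design effect: DE = 1 + (m − 1) × ICC
- Naive SE / true SE = 1/√DE
- True two-sided error = 2 × [1 − Φ(1.96/√DE)]

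Example, m = 2 and ICC = 0.3: DE = 1.3; SE ratio = 1/√1.3 = 0.88; 1.96/√1.3 = 1.72; error = 8.6%.

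| m | ICC | DE | Naive/true SE | True error at nominal 5% |
|---|---|---|---|---|
| 1 | any | 1.00 | 1.00 | 5.0% |
| 1.25 | 0.1–0.8 | 1.025–1.20 | 0.99–0.91 | 5.3–7.4% |
| 1.5 | 0.3–0.5 | 1.15–1.25 | 0.93–0.89 | 6.8–8.0% |
| 2 | 0.3–0.7 | 1.3–1.7 | 0.88–0.77 | 8.6–13.3% |
| 3 | 0.3–0.7 | 1.6–2.4 | 0.79–0.65 | 12.1–20.6% |

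**Stepwise selection and the treatment standard error.** A logistic simulation with no treatment effect used 1,500 runs per setting, eight baseline covariates (two of them related to union) and the forward 0.05 / backward 0.10 rule. Treatment was then added to the selected model. N was 112 (protocol) or 200 (application). Fractures per patient, where more than one was allowed, averaged 1.7. Monte Carlo error is √(0.05 × 0.95/1,500), about 0.006.

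| Records analysed | N | Type I error, treatment | Mean SE / empirical SD |
|---|---|---|---|
| One per patient | 112 | 0.067 | 0.92 |
| One per patient | 200 | 0.042 | 1.02 |
| Fractures, latent ICC about 0.5, clustering ignored | 112 | 0.092 | 0.86 |
| Fractures, latent ICC about 0.5, clustering ignored | 200 | 0.103 | 0.85 |
| Fractures, no residual correlation | 112 | 0.051 | 0.98 |
| Fractures, no residual correlation | 200 | 0.044 | 1.02 |

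Selection is present in all six rows. The loss is consistent only where clustering is present and ignored. The 0.067 at N = 112 is not separated from ordinary small-sample error of logistic regression, and it does not recur at N = 200.

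**What selection does affect.** With independent null candidates and entry at p < 0.05, the chance that at least one enters is 1 − 0.95^10 = 0.40 for 10 candidates and 1 − 0.95^15 = 0.54 for 15. The number of candidates is assumed. These figures concern the clinical factors, not the arm comparison.

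**The case against.** The strongest reply is that Aim 3 is under-specified rather than wrong. A reader might infer that it counts fractures instead of patients. The text says when a fracture is united but does not name the unit of analysis, and an index-fracture or patient-level analysis is compatible with it. Fracture-level analysis is the natural reading, not a stated fact. Eligibility (protocol section 5) requires NISS above 9, not several fractures or even one, and the word polytrauma comes from an interim abstract. The range must therefore start at no inflation. All of this stands.

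A reader might also infer that stepwise selection itself makes the treatment standard error too small. The simulation does not support that. Nor do the documents suggest that treatment could be dropped: selection is applied to baseline clinical factors, and the final model is described as between two groups. Treatment is simply not stated to be forced in.

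Finally, union may no longer be an outcome. The application's Objectives list only Aims 1 and 2. Union is absent from protocol section 3, from section 7 and from the rows of the section 9 schedule, and section 9 ends participation at the 6-week visit, before the first union time point. This reduces the weight of the point but does not remove it: Aim 3 is in the current application, section 15 still claims union as something the trial will evaluate, and the schedule has columns to 12 months.

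**Conclusion.** The point holds in conditional form. Aim 3 states a between-arm comparison of union worded per fracture, with no rule for several fractures in a patient, no clustering adjustment and data-driven covariates. If fractures are analysed as independent, the true error at a nominal 5% runs from 5.0% (one fracture per patient) to 20.6% (three, ICC 0.7). The position in that range rests on fractures per patient and an ICC that the documents do not give. With one record per patient, or with clustering modelled, this loss disappears. It cannot be said that the standard error will be too small.

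The stepwise rule is a second, independent fault. Its costs are a model that is not prespecified and over-optimistic p-values for the selected factors. The point should be corrected before union is analysed, but it concerns an aim outside the protocol's outcome list and does not touch the primary outcome.

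**What to change.** First, reconcile the status of union across Aim 3, the Objectives, and protocol sections 3, 7, 9 and 15, including the end of participation against the 12-month schedule.

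If union stays as an outcome:

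- Delete the stepwise step.
- State that treatment is forced into the model.
- Fix the covariates in advance, for example from the baseline factors already listed for Aim 1 (age, sex, injury severity, head or extremity injury severity, mechanism). Leave out that list's injury outcome, because it arises after randomisation.
- Choose one unit: a patient-level outcome (all study fractures united), or a fracture-level GEE clustered on patient with robust standard errors. Define which fractures count, and say how the three visits enter.
- Report the difference in union between arms with its 95% CI.

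The cost is analysis text, which must be added to section 7 because it has no union analysis to amend. No new data are needed if union is recorded by fracture and patient. Intervals will be wider wherever patients have several correlated fractures. The patient-level outcome is simpler but discards partial healing. Enrolment is closed, but the interim results shown cover opioid intake and pain only, so the documents show no union result that would stand in the way of fixing this now.
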